### **3.3 Expansion Cohort Specific Inclusion Criteria**

3.3.1 Patients must have had progressive disease on prior first line EGFR inhibitor therapy with osimertinib.

### **3.4 Restrictions**

3.4.1 Telaglenastat (CB-839) HCl is a weak *in vitro* inhibitor of CYP2C9. Therefore, patients receiving any medications or substances that are substrates of CYP2C9 are eligible but should use caution with substrates that have a narrow therapeutic index. Because the lists of these agents are constantly changing, it is important to regularly consult a frequently-updated medical reference. As part of the enrollment/informed consent procedures, the patient will be counseled on the risk of interactions with other agents, and what to do if new medications need to be prescribed or if the patient is considering a new over-the-counter medicine or herbal product.

3.4.2 The effects of Telaglenastat (CB-839) HCl and Osimertinib (AZD9291) on the developing human fetus are unknown. For this reason and because glutaminase inhibitor and EGFR TKI agents are known to be teratogenic, women of child-bearing potential must agree to use adequate contraception (hormonal or barrier method of birth control; abstinence) prior to study entry, for the duration of study participation, and up to 6 weeks after receiving last dose of study treatment. Should a woman become pregnant or suspect she is pregnant while she or her partner is participating in this study, she should inform her treating physician immediately. Men treated or enrolled on this protocol must also agree to use adequate contraception prior to the study, for the duration of study participation, and 4 months after completion of Telaglenastat (CB-839) HCl and Osimertinib (AZD9291) administration. For further details please refer to Appendix F (Definition of Women of Childbearing Potential and Acceptable Contraceptive Methods).

3.4.3 Patients who have received prior treatment with immune-oncology (IO) therapies should be closely monitored for an appropriate period of time after the last dose of the IO treatment, in accordance with the respective IO label, as immune mediated adverse reactions with the IO therapy may occur at any time during or after discontinuation of therapy. The stop date of the prior IO drug therapy should be captured in the case report forms.

3.4.4 In patients with resolved or chronic hepatitis B infection (inactive carrier state) or active controlled HBV infection on treatment with osimertinib:

- a. Recommend monthly monitoring of ALT/AST, HBV DNA levels and HBsAg (if negative at baseline)
- b. Where liver signs and symptoms of viral reactivation appear (HBV DNA levels exceeding 10-fold from baseline or  $\geq 100$  IU/ml (if baseline HBV DNA levels are undetectable) or conversion of HBsAg negative to positive):

Expert hepatologist/specialist oversight of the patient is required. Consider interruption

or discontinuation of study treatment, based on risk-benefit assessment

- 3.4.5 In terms of reproductive restrictions, the use of osimertinib in the approved setting needs to follow the current approved local safety guidance.
- 3.4.6 Once enrolled all patients must try to avoid concomitant use of medications, herbal supplements and/or ingestion of foods that are known to be strong inducers of CYP3A4 whenever feasible, but patients may receive any medication that is clinically indicated for treatment of adverse events. Such drugs must have been discontinued for an appropriate period before they enter screening and for a period of 3 months after the last dose of Osimertinib (AZD9291). All concomitant medications should be captured on the eCRF. Guidance on medicines to avoid, medications that require close monitoring and on washout periods is provided (see Appendix A).

If medically feasible, patients taking regular medication, with the exception of potent inducers of CYP3A4 (see above), should be maintained on it throughout the study period. Patients taking concomitant medications whose disposition is dependent upon BCRP and/or P-glycoprotein (P-gp) and which have a narrow therapeutic index should be closely monitored for signs of changed tolerability as a result of increased exposure of the concomitant medication whilst receiving Osimertinib (AZD9291). Guidance on medications to avoid, medications that require close monitoring and on washout periods is provided (see Appendix D “Guidance regarding Potential Interactions with Concomitant Medications”).

Patients taking rosuvastatin should have creatine phosphokinase levels monitored (due to BCRP-mediated increase in exposure). If the patient experiences any potentially relevant AEs suggestive of muscle toxicity including unexplained muscle pain, tenderness, or weakness, particularly if accompanied by malaise or fever, rosuvastatin must be stopped and any appropriate further management should be taken.

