### Acceptable Contraception Methods:

Highly effective method of birth control is defined in Note 3 in International Conference on Harmonisation Guidance M3 (Nonclinical Safety Studies for the Conduct of Human Clinical Trials for Pharmaceuticals) as one that results in a low failure rate (e.g., less than 1 percent per year) when used consistently and correctly.

Note that women should have been stable on their chosen method of birth control for a minimum of 2 weeks before entering the trial. Generic names and examples of trade names are given. As trade names may vary, Investigators should check the generic name of any contraception to ensure suitability.

Acceptable contraception methods are:

- Total sexual abstinence (abstinence must be for the total duration of the trial and the follow-up period)
- Vasectomised sexual partner plus male condom (with participant assurance that partner received post-vasectomy confirmation of azoospermia)
- Tubal occlusion plus male condom

- Intra-uterine device – provided coils are copper-banded, plus male condom
- Intra-uterine system (IUS) levonorgestrel IUS (e.g., Mirena), plus male condom
- Medroxyprogesterone injections (Depo-Provera) plus male condom
- Etonogestrel implants (e.g., Implanon, Norplan) plus male condom
- Normal and low dose combined oral contraceptive pills, plus male condom
- Norelgestromin / ethinylestradiol transdermal system plus male condom
- Intravaginal device (e.g., ethinylestradiol and etonogestrel) plus male condom
- Cerazette (desogestrel) plus male condom (Cerazette is currently the only highly efficacious progesterone based pill)

Unacceptable Contraception Methods:

The following methods are considered not to be highly effective and are therefore not acceptable contraceptive methods in AstraZeneca clinical trials:

- Triphasic combined oral contraceptives
- All progesterone only pills except, Cerazette
- All barrier methods, if intended to be used alone
- Non-copper containing intra-uterine devices
- Fertility awareness methods
- Coitus interruptus

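### Section 3.4.2 accepts a hormonal or barrier contraceptive on its own for women of childbearing potential; Appendix F does not, and no sentence says which prevails.

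*Combined protocol and SAP*

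**What the plan says.** Section 3.4.2 requires women of childbearing potential to use adequate contraception before entry, during participation and for up to 6 weeks after the last dose. It describes what counts as "hormonal or barrier method of birth control; abstinence". Men must use adequate contraception until 4 months after treatment ends; the sentence about them names no method. The paragraph closes with "For further details please refer to Appendix F".

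Appendix F has two lists. The acceptable list pairs hormonal methods with a condom, for example "Normal and low dose combined oral contraceptive pills, plus male condom" and "Medroxyprogesterone injections (Depo-Provera) plus male condom". It also includes total abstinence. The unacceptable list includes "All barrier methods, if intended to be used alone", "Triphasic combined oral contraceptives" and "All progesterone only pills except, Cerazette". Its lead-in calls these methods not highly effective and therefore "not acceptable contraceptive methods in AstraZeneca clinical trials".

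Section 8.1.1, under patient care implications for telaglenastat, asks for two effective forms of contraception during telaglenastat treatment. It does not mention abstinence.

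**The concern.** Section 3.4.2 sits with the patient-selection rules and is where a site would look first. Its wording needs one method only, hormonal or barrier. Appendix F accepts neither kind on its own. The cross-reference offers the appendix as further detail and does not say that it overrides the parenthetical.

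Section 3.4.2 gives as the reason for the rule that both agent classes are known teratogens. Under section 10.5, a pregnancy on study means stopping the investigational product immediately and reporting within 24 hours, and the reporting duty extends to 6 weeks after the final dose. A rule meant to prevent that outcome should have one meaning.

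**Working it through.** No plan figure needs reproducing. The check is a count of the Appendix F lists, set against sections 3.4.2 and 8.1.1.

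**Acceptable list in Appendix F**

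- Hormonal, each with a male condom: levonorgestrel intra-uterine system, medroxyprogesterone injection, etonogestrel implant, combined pill, transdermal system, intravaginal device, Cerazette = 7.
- Non-hormonal, each with a male condom: vasectomised partner, tubal occlusion, copper intra-uterine device = 3.
- Total abstinence = 1.
- Total: 7 + 3 + 1 = 11. With a condom: 7 + 3 = 10. Hormonal or barrier method used alone: 0.

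**Unacceptable list in Appendix F**

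There are 6 entries. Three fit the words hormonal or barrier: triphasic pills, progesterone-only pills other than Cerazette, and barrier methods alone. The other three are non-copper intra-uterine devices, fertility awareness and coitus interruptus.

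**Side by side**

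| Method | Section 3.4.2 as worded | Appendix F | Section 8.1.1 |
|---|---|---|---|
| Barrier alone | accepted | rejected expressly | one form, not enough |
| Triphasic pill alone | accepted | rejected expressly | one form, not enough |
| Progesterone-only pill other than Cerazette, alone | accepted | rejected expressly | one form, not enough |
| One of the 7 listed hormonal methods, no condom | accepted | not on the acceptable list | one form, not enough |
| One of the 7 with a male condom | accepted | accepted | two forms |
| One of the 3 non-hormonal methods with a male condom | accepted (condom is a barrier) | accepted | two forms |
| Total abstinence | accepted | accepted | not mentioned |

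**Reading the table**

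1. From Appendix F to section 3.4.2: all 11 accepted methods pass, 10 because they include a condom and 1 because it is abstinence.
2. From section 3.4.2 to Appendix F: the first four rows fail. Three are ruled out in so many words. The fourth is ruled out by omission, because no hormonal method is listed without a condom.
3. Section 8.1.1 agrees with Appendix F in every row except abstinence, where it is silent.

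**Does another sentence settle precedence?**

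- Section 3.4.5 refers to local guidance for osimertinib in its approved setting. This trial gives an investigational combination, so that sentence does not decide the matter.
- The lead-in to the unacceptable list refers to one company's trials, whereas section 10.3.2 names NCI as sponsor. That company supplies osimertinib (section 8.1.2), so the list is evidently meant to apply here, but no sentence says so.

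**The case against.** The best defence is that section 3.4.2 is shorthand and sends the reader, in the same paragraph, to an appendix whose title announces acceptable contraceptive methods. A careful site would find the stricter list. Following that list always complies with section 3.4.2 as well, so no woman receives incompatible instructions. This stands, and it limits the point to one text being looser than the other. It does not remove the point: section 3.4.2 names a barrier method as adequate, the appendix rejects barrier methods used alone, and a pointer to further detail does not say which text wins.

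Two stronger readings are tempting, and the documents support neither.

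- A reader might infer that abstinence is the only method meeting both texts, or that requiring a condom alongside a hormonal method contradicts section 3.4.2. Section 3.4.2 sets a minimum and does not forbid using both. A pill with a condom satisfies both texts, as do all 11 methods.
- A reader might infer a three-way conflict with section 8.1.1. Ten of the 11 Appendix F methods already pair a method with a condom, so the two-form rule broadly agrees with the appendix. The gap is its silence on abstinence. It also applies only during telaglenastat treatment, which section 6.1 ends on 2/28/25.

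The closure of accrual, recorded in the summary of changes, narrows the scope too. It does not end the duty, which continues through participation and 6 weeks beyond. Section 6.1 lets patients stay on osimertinib alone after telaglenastat stops. From then on the two-form rule no longer applies, and only section 3.4.2 and Appendix F remain.

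**Conclusion.** The point holds as a one-way mismatch. Section 3.4.2 lets through 3 methods that Appendix F expressly rejects, and any of 7 hormonal methods without the condom that the appendix attaches. Nothing in the reverse direction fails, and no text states precedence.

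The consequence is for participant safety only. No endpoint, dose decision, sample size or analysis changes. Planned accrual is at most 28 patients (section 9.2), and those still in scope are women of childbearing potential on treatment or within 6 weeks of their last dose. That number is not given and cannot be derived.

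The conclusion rests on reading the parenthetical in section 3.4.2 literally. It concerns the protocol text, not what patients were told, because the consent pages are not in the copy reviewed. It is a wording correction worth making, since the possible harm is to a fetus and the remedy is short.

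**What to change.** Make three wording changes.

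1. In section 3.4.2, replace the parenthetical with *(a method listed as acceptable in Appendix F)* and add: *For women of childbearing potential, Appendix F governs for the duration of study participation and for 6 weeks after the last dose of study treatment.* The opening words matter. The same paragraph sets 4 months for men, and an unrestricted sentence could be read as cutting that to 6 weeks. Leave the rule for men unchanged.
2. In section 8.1.1, replace the two-form requirement with a pointer to the Appendix F list. This also makes clear that abstinence is acceptable there.
3. In Appendix F, reword the lead-in to the unacceptable list so that it refers to this trial.

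The cost is the three edits and a notice to sites. Visits, data collection, analysis and sample size stay as they are. The change clarifies a continuing conduct rule using the protocol's own list; with accrual closed, it does not reopen entry for anyone.

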### **3.5 Inclusion of Women and Minorities**

National Institute of Health (NIH) policy requires that women and members of minority groups and their subpopulations be included in all NIH-supported biomedical and behavioral research projects involving NIH-defined clinical research unless a clear and compelling rationale and justification establishes to the satisfaction of the funding Institute & Center (IC) Director that inclusion is inappropriate with respect to the health of the subjects or the purpose of the research. Exclusion under other circumstances must be designated by the Director, NIH, upon the recommendation of an IC Director based on a compelling rationale and justification. Cost is not an acceptable reason for exclusion except when the study would duplicate data from other sources. Women of childbearing potential should not be routinely excluded from participation in clinical research. Please see <http://grants.nih.gov/grants/funding/phs398/phs398.pdf>.

## **4. REGISTRATION PROCEDURES**

#### 4.1 Investigator and Research Associate Registration with CTEP

Food and Drug Administration (FDA) regulations and National Cancer Institute (NCI) policy require all individuals contributing to NCI-sponsored trials to register and to renew their registration annually. To register, all individuals must obtain a Cancer Therapy Evaluation Program (CTEP) Identity and Access Management (IAM) account at <https://ctepcore.nci.nih.gov/iam>. In addition, persons with a registration type of Investigator (IVR), Non-Physician Investigator (NPIVR), or Associate Plus (AP) (*i.e.*, clinical site staff requiring write access to Oncology Patient Enrollment Network (OPEN), Rave, or acting as a primary site contact) must complete their annual registration using CTEP's web-based Registration and Credential Repository (RCR) at <https://ctepcore.nci.nih.gov/rcr>.

RCR utilizes five person registration types.

- IVR: MD, DO, or international equivalent,
- NPIVR: advanced practice providers (*e.g.*, NP or PA) or graduate level researchers (*e.g.*, PhD),
- AP: clinical site staff (*e.g.*, RN or CRA) with data entry access to CTSU applications (*e.g.*, Roster Update Management System [RUMS], OPEN, Rave, ),
- Associate (A): other clinical site staff involved in the conduct of NCI-sponsored trials, and
- Associate Basic (AB): individuals (*e.g.*, pharmaceutical company employees) with limited access to NCI-supported systems.

RCR requires the following registration documents:

Documentation Required	I V R	N P I V R	A P	A	A B
FDA Form 1572	✓	✓			
Financial Disclosure Form	✓	✓	✓		
NCI Biosketch (education, training, employment, license, and certification)	✓	✓	✓		
GCP training	✓	✓	✓		
Agent Shipment Form (if applicable)	✓				
CV (optional)	✓	✓	✓		

An active CTEP-IAM user account and appropriate RCR registration is required to access all CTEP and Cancer Trials Support Unit (CTSU) websites and applications. In addition, IVRs and NPIVRs must list all clinical practice sites and Institutional Review Boards (IRBs) covering their practice sites on the FDA Form 1572 in RCR to allow the following:

NCI Protocol #: 10216

Version Date: 09/17/2024

- Addition to a site roster,
- Assign the treating, credit, consenting, or drug shipment (IVR only) tasks in OPEN,
- Act as the site-protocol Principal Investigator (PI) on the IRB approval, and
- Assign the Clinical Investigator (CI) role on the Delegation of Tasks Log (DTL).

In addition, all investigators act as the Site-Protocol PI, consenting/treating/drug shipment, or as the CI on the DTL must be rostered at the enrolling site with a participating organization (*i.e.*, Alliance).

Additional information is located on the CTEP website at

<https://ctep.cancer.gov/investigatorResources/default.htm>. For questions, please contact the RCR Help Desk by email at [contact].

## 4.2 Site Registration

This study is supported by the NCI Cancer Trials Support Unit (CTSU).

### IRB Approval

Sites participating with the NCI Central Institutional Review Board (NCI CIRB) must submit the Study Specific Worksheet for Local Context (SSW) to the CIRB using IRBManager to indicate their intent to open the study locally. The NCI CIRB's approval of the SSW is automatically communicated to the CTSU Regulatory Office, but sites are required to contact the CTSU Regulatory Office at [[contact]](mailto:[contact]) to establish site preferences for applying NCI CIRB approvals across their Signatory Network. Site preferences can be set at the network or protocol level. Questions about establishing site preferences can be addressed to the CTSU Regulatory Office by emailing the email address above or calling [name].

In addition, the Site-Protocol PI (*i.e.*, the investigator on the IRB/REB approval) must meet the following five criteria to complete processing of the IRB/REB approval record:

- Holds an Active CTEP status,
- Rostered at the site on the IRB/REB approval (*applies to US and Canadian sites only*) and on at least one participating roster,
- If using NCI CIRB, rostered on the NCI CIRB Signatory record,
- Includes the IRB number of the IRB providing approval in the Form FDA 1572 in the RCR profile, and
- Holds the appropriate CTEP registration type for the protocol.

### Additional Requirements

Additional requirements to obtain an approved site registration status include:

- An active Federalwide Assurance (FWA) number,
- An active roster affiliation with the Lead Protocol Organization (LPO) or a Participating Organization, and

Compliance with all protocol-specific requirements (PSRs).

#### 4.2.1 Downloading Regulatory Documents

Download the site registration forms from the protocol-specific page located on the CTSU members'

NCI Protocol #: 10216

Version Date: 09/17/2024

website. Permission to view and download this protocol and its supporting documents is restricted based on person and site roster assignment. To participate, the institution and its associated investigators and staff must be associated with the LPO or a Participating Organization on the protocol.

- Log on to the CTSU members' website (<https://www.ctsu.org>) using your CTEP-IAM username and password,
- Click on *Protocols* in the upper left of your screen
  - Enter the protocol number in the search field at the top of the protocol tree, or
  - Click on the By Lead Organization folder to expand, then select LAO-OH007, and protocol number 10240,
- Click on *Documents*, select *Site Registration*, and download and complete the forms provided. (Note: For sites under the CIRB initiative, IRB data will load automatically to the CTSU as described above.)

#### 4.2.2 Requirements For NCI 10216 Site Registration

- Site Initiation Teleconference
- Specimen Tracking System Training Requirement:
  - All data entry users (Clinical Research Associate role) at each participating site will need to complete the Theradex-led training.
  - Theradex will provide a certificate of completion, which will need to be submitted to the CTSU through the Regulatory Submission Portal.
  - The training is a one-time only requirement per individual. If an individual has previously completed the training for another ETCTN study, the training does not need to be completed again nor does the certificate of completion need to be resubmitted to the CTSU. However, new versions of the Specimen Tracking System may require new training.
  - This training will need to be completed before the first patient enrollment at a given site.
  - Please contact STS Support at Theradex for the training ([[contact]](mailto:[contact]), Theradex [contact]).

#### 4.2.3 Submitting Regulatory Documents

Submit required forms and documents to the CTSU Regulatory Office via the Regulatory Submission Portal on the CTSU website.

To access the Regulatory Submission Portal, log on to the CTSU members' website → Regulatory → Regulatory Submission.

Institutions with patients waiting that are unable to use the Regulatory Submission Portal should alert the CTSU Regulatory Office immediately at [name] in order to receive further instruction and support.

NCI Protocol #: 10216

Version Date: 09/17/2024

#### 4.2.4 Checking Site Registration Status

You can verify your site's registration status on the members' side of the CTSU website.

- Log on to the CTSU members' website
- Click on *Regulatory* at the top of your screen
- Click on *Site Registration*
- Enter your 5-character CTEP Institution Code and click on Go

Note: The status shown only reflects institutional compliance with site registration requirements as outlined above. It does not reflect compliance with protocol requirements for individuals participating on the protocol or the enrolling investigator's status with the NCI or their affiliated networks.

